9.3 Patient instruction and consent forms

Every patient will receive a complete and comprehensive explanation of the significance, nature, extent and possible risks of the trial. To this end a detailed, written patient information sheet will be made available. In addition a physician will carry out an oral information session during which the patients will be given sufficient time and opportunity to clarify remaining questions. Two identical forms for written informed consent will be given to the patients for signature. One copy of the signed forms will be archived in the investigator file and the other retained by the patient.

The investigator will acknowledge instruction of every patient in accordance with the clinical trial protocol and the existence of a signed consent form.

9.4 Data protection

During the clinical trial medical and personal information (like age, gender, racial, and ethnic origin) will be collected at the site and documented in the personal file or electronically saved. In addition, important data for the clinical trial (including photos and PK data of the subgroups) will be saved pseudonymized, transferred, and evaluated.

If necessary, the collected and saved data (including the photos and PK data) during the clinical trial will be held for inspection by the supervisory authority or by people charged by the sponsor who check that the trial is done properly. If needed, the related data will be shared pseudonymized to:

- The sponsor or sponsor-appointed party for the purpose of scientific analysis;
- The applicant and the authority responsible for marketing authorization, in case that application for marketing authorization is requested;
- Sponsor and the responsible competent authority, which will also forward the data to the European database, in case of adverse events of the trial drug;
- Parties in Europe and in non-European foreign countries which are affiliates of the Sponsor and as well forwarded to the responsible authorities in charge of marketing authorization by the latter.

Personal and medical data collected during the trial may be moved, stored and used in the EU or another country where the sponsor or those working with the sponsor located. Data – including trial results – might be published in Scientific Journals, Conference abstract, etc. The trial and trial data will be published in clinicaltrials.gov.

9.5 Termination of participation

Every patient has the right to refuse further participation in the trial at any point in time and without giving reasons. Nonetheless, efforts should be made to find out the cause and to document it on the case report form. If the administration of the investigational product has already taken place at the time of refusal, the patient should be convinced to consent to a complete final examination as planned in the protocol in his/her own interest. This has to be documented on the corresponding pages of the eCRF.

9.6 Quality control (Trial monitoring)

According to bioskin quality management procedures internal quality control will be applied to all steps of the trial e.g. planning, conduct, analysis and reporting.

A representative of sponsor or bioskin will monitor the trial progress as regularly as necessary during the conduct of the trial until the last case report forms have been completed and all queries have been resolved.

The trial and site activities will be monitored according to the ICH-GCP guidelines for:

- Protocol adherence (trial is conducted in accordance with the currently approved protocol and any other trial agreements)
- Quality of data (data are authentic, accurate, and complete)
- Drug accountability
- Protection of safety and rights of patients
- Compliance with regulatory requirements (trial is conducted in accordance with GCP, and all applicable regulatory requirements)
- Adequacy of the facilities (unchanged high qualification of the site and site staff)

The investigators and the head of the medical institutions (where applicable) agree to allow the monitor direct access to all relevant documents.

9.7 Quality assurance

To ensure compliance with GCP and all applicable regulatory requirements Sponsor may conduct a quality assurance assessment and/or audit of the site records at any time during or after completion of the trial.

Auditing will be performed by or on behalf of Quality Assurance MetrioPharm in accordance with the requirements of Note for Guidance on Good Clinical Practice, the clinical trial protocol, applicable standard operating procedures and according to the agreed audit plan.

All audit activities in the course of MP1032-CT04 will be documented and archived.

Independent of any sponsor audit the regulatory agencies may conduct a regulatory inspection at any time during or after completion of the trial.

In the event of an assessment, audit or inspection, the investigators (and institutions) must agree to grant the advisor(s), auditor(s) and inspector(s) direct access to all relevant documents and to allocate their time and the time of their staff to discuss the conduct of the trial, any findings/relevant issues and to implement any corrective and/or preventative actions to address any findings/issues identified.

- [4] World Health Association Declaration of Helsinki. Ethical Principles for Medical Research involving Human Patients. Adopted by the 18th WMA General Assembly, Helsinki, Finland, June 1964, and amended by the 48th WMA General Assembly, Somerset West, Republic of South Africa, October 1996.
- [5] Note for Guidance on Good Clinical Practice (CPMP/ICH/135/95). The European Agency for the Evaluation of Medicinal Products (EMEA) 2002;1-59.

**Appendix A
Trial flow chart**

Trial flow chart

Trial Period	Screening	Treatment phase				Follow-up	Unscheduled visit
Day	(Day - 28 to -3)	Day 1	Day 28 (±2 days)	Day 56 (±2 days)	Day 84 (+5 days)	Day 112 (±2 days)	
Visit Number	1	2	3	4	5	6	unscheduled
Procedure							
Informed consent	X						
In-/exclusion criteria	X	X					
Demographics/medical history	X						
Physical examination	X	X			X	X	
Height, body weight, BMI	X						
Smoking history/ alcohol consumption	X						
Vital signs	X	X	X	X	X	X	
Pregnancy test in female patients ^a	X	X ^b			X		
Safety laboratory, incl. urine dipstick	X	X	X	X	X	X	X
HIV, Hepatitis	X						
Randomization		X					
Localization of photographic documentation test field^c		X					
Photographic documentation^c		X	X	X	X	X	
PK sample ^d		X			X		
PASI	X	X	X	X	X	X	
PGA	X	X	X	X	X	X	
BSA	X	X	X	X	X	X	
Dispensing of IMP		X	X	X			
IMP administration ^e		X	X	X	X		
Diary dispensing		X	X	X			
Drug return / accountability			X	X	X		
Diary return and check			X	X	X		
Prior and concomitant therapy	X	X	X	X	X	X	X
Adverse events ^f	X	X	X	X	X	X	X

a) A serum pregnancy test will be done for all women at screening and urine test for all other visits.

b) A urine pregnancy test on Day 1 will be performed prior to the first administration of IMP for all women.

c) Only performed in a subgroup of approx. 2 sites (approx. 30 patients); on Day 1 Photographic

- d) documentation will be performed prior to the first administration of IMP
Only performed in a subgroup of approx. 4 sites (approx. 30 patients); on Day 1 and Day 84 first PK sample will be performed prior to the first administration of IMP. PK samples will be collected before IMP administration, and 15, 30, 60 and 120 minutes after administration of IMP.
- e) IMP administration will start on Day 1 after randomization and will continue as self-administration by trial patients at home until Day 84. Patients included in the PK analysis will administrate the first treatment (Day 1) at the site. All patients will administrate the last treatment (Day 84) at the sites.
- f) AE reporting starts after the signature of informed consent form and finishes at the End of Study Follow-Up Visit.

**Appendix B
PASI**

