5.3.2 Inclusion criteria

All of the following criteria have to be met for inclusion of a patient in this trial:

1. Participants legally competent to sign and give informed consent.
2. Adult male and female patients between 18 years and 70 years with moderate-to-severe chronic plaque psoriasis (diagnosed by Investigator):
 - a) PASI score ≥ 10 - ≤ 20 at baseline
 - b) BSA score: $> 10\%$
 - c) Stable disease duration of ≥ 6 months at the initiation of IMP.
 - d) topical therapy fails to control the disease
3. Body Mass Index (BMI) between 18.5 and 34.9 kg/m².
4. Women of childbearing potential (WCBP) must have a negative serum pregnancy test at Screening (Visit 1). In addition, sexually active WCBP must agree to use adequate contraception throughout the trial (see Section 3.2 for more details on adequate contraception):
 - a) A method with less than 1% failure rate OR
 - b) Abstinence
5. Post-menopausal women with spontaneous amenorrhea for at least 12 months and women on hormonal replacement therapy (HRT). The use of hormonal replacement therapy (HRT) during the trial is permitted, however for these patients an appropriate contraception method according to Inclusion Criterion 4 must be ensured. Sterilized women may be included (see Section 3.2 for more details on sterile definition)
6. Male patients who are sexually active with a female partner and are not surgically sterile (vasectomy performed at least six months prior to treatment) must agree to inform their female sexual partner to use an acceptable form of birth control as described in the informed consent form. For females, an acceptable method (Pearl Index < 1%) would be to use implants, injectable, combined oral contraceptives, some intrauterine devices, or be postmenopausal, be surgically sterile (hysterectomy, bilateral tubal ligation, or bilateral oophorectomy)
7. In good health as judged by the investigator, based on medical history, physical examination, serum chemistry, hematology and urinalysis
8. Patients must meet the following clinical laboratory criteria:

- White blood cell count $\geq 3.5 \times 10^9/L$
- Platelet count $\geq 100 \times 10^9/L$
- Serum creatinine $\leq 1.5 \times$ upper limit of normal (ULN); estimated glomerular filtration rate $> 60 \text{ mL/min}$
- Total bilirubin $\leq 1.5 \times \text{ULN}$
- Aspartate aminotransferase (AST) and alanine aminotransferase (ALT) $\leq 2.5 \times \text{ULN}$

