5.3.5.2 Criteria for discontinuing in the case of individual patients

Patients may withdraw from the entire trial including follow-up at any time without penalty and for any reason without prejudice to his or her future medical care.

The following criteria must lead to discontinuation from the clinical trial in individual patients:

- Patient withdraws informed consent

- Pregnancy (see section 7.4)
- Severe protocol violations that result in a significant risk to the patient's safety
- Emergence of the following AEs including:
 - a) Patient reports symptoms which are considered unacceptable by the patient or the Investigator or if any serious AE occurs that is judged as at least possibly related to the IMP by the Investigator
 - b) Abnormal laboratory value(s) confirmed by repeat measurements:
 - Elevated liver transaminases (AST/ALT) $\geq 3 \times$ ULN AND elevated bilirubin total bilirubin $\geq 2 \times$ ULN
 - Elevated serum creatinine $\geq 2 \times$ ULN

The following criteria may lead to discontinuation from the clinical trial in individual patients:

- Use of prohibited concomitant medication as defined in section 5.4.5.

In all cases, the reason(s) for withdrawal, and the primary reason, must be recorded on the electronic data capture (EDC) system / electronic case report form (eCRF). If a patient is prematurely withdrawn from the IMP for any reason, the Investigator must make every effort to perform the evaluations described for the End of Treatment and Follow-up Visits. The Investigator should contact the Medical Monitor, whenever possible, to approve withdrawal of patients in advance.

If a patient withdraws consent and still agrees to undergo a final examination, it will be documented on the eCRF and the patient record.

A patient may also be withdrawn from the IMP by the Sponsor, Regulatory Authorities, or Independent Ethics Committees (IECs) / Institutional Review Boards (IRBs).

Patients who are withdrawn from the trial will be not replaced.

Protocol violation, failure to comply with the trial stipulations/poor compliance may lead to discontinuation from the clinical trial in individual patients.

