5.4 Treatments

The IMP will be packed in kits, 1 kit per patient per week. One kit contains 14 blisters and one blister contains six, 50 mg, hard gelatin capsules of MP1032 and/or placebo (described below).

IMP will be packaged and labelled by **CC1** according to all local legal requirements. IMP will be labelled in accordance with applicable regulatory requirements.

All IMP supplies must be stored at room temperature (15 - 25°C) and protected from light, in accordance with the manufacturer's instructions. Until dispensed to the patients, the IMP will be stored in a securely locked area, accessible to authorized personnel only.

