5.5 Efficacy and safety variable(s)

5.5.1 Procedures

Screening period

Day -28 to -3 (visit 1)

Within the 28 days prior to the first IMP administration the volunteer will come to the trial centers for the initial screening (including documentation of demographic data). Screening assessments will be performed after the volunteer has agreed to participate and has signed and dated the informed consent form.

At screening a serum pregnancy test will be carried out in all female patients.

The following examinations will be performed:

- Obtain written informed consent
- Documentation of relevant medical and relevant surgical history (last 5 years)
- Documentation of demographic data
- Documentation of Smoking history/ alcohol consumption
- Documentation of relevant previous medication (last 6 weeks)
- Serum pregnancy test and urinalysis (see section 5.5.2)
- Start check in-/exclusion criteria (see section 5.3.2 and 5.3.3)
- Physical examination (see section 5.5.5)
- Height, body weight and BMI
- Record vital signs (see section 5.5.3)
- PASI (see section 5.5.1.1)
- PGA (see section 5.5.1.2)
- BSA (see section 5.5.1.3)

- Collection of samples for determination of laboratory parameters (serology, hematological status, clinical chemistry, see section 5.5.2).

Note: Adverse events before start of treatment (i.e. occurring after signature on consent form). Patients who have abnormal test results during the screening period may be re-screened if the Medical Monitor agrees.

Experimental phase

Trial Day 1 (baseline, week 1, visit 2)

- Re-check of in-/exclusion criteria (see section 5.3.2)
- Randomization
- Physical examination (see section 5.5.5)
- Record vital signs (see section 5.5.3)
- Urine pregnancy test and urinalysis (see section 5.5.2)
- Record concomitant medications
- Record adverse events occurring from the time of informed consent signature
- *Localization of photographic documentation test field only for a subgroup (see section 5.5.1.4)*
- *Photographic documentation only for a subgroup (see section 5.5.1.4)*
- Collection of samples for determination of laboratory parameters (hematological status, clinical chemistry, see section 5.5.2)
- PASI (see section 5.5.1.1)
- PGA (see section 5.5.1.2)
- BSA (see section 5.5.1.3)
- Dispensing diary
- *Start of PK samples only for a subgroup (see section 5.5.1.5)*
- Dispensing IMP
- *Administration of IMP at site (PK subgroup only)*

Trial Day 28 (week 4, visit 3) and Day 56 (week 8, visit 4)

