- Check concomitant therapy and adverse events
- Record vital signs
- Drug return / accountability and re-dispensation of unused kits/blister
- Diary collected and checked
- *Photographic documentation only for a subgroup (see section 5.5.1.4)*
- Urinalysis (see section 5.5.2)
- Collection of samples for determination of laboratory parameters (hematological status, clinical chemistry, urinalysis, see section 5.5.2)
- PASI (see section 5.5.1.1)

- PGA (see section 5.5.1.2)
- BSA (see section 5.5.1.3)
- Dispensing of IMP and diary

Trial Day 84 (week 12, visit 5) (EoT)

- Check concomitant therapy and adverse events
- Physical examination (see section 5.5.5)
- Record vital signs (see section 5.5.3)
- Urine pregnancy test and urinalysis (see section 5.5.2)
- *Photographic documentation only for a subgroup (see section 5.5.1.4)*
- Collection of samples for determination of laboratory parameters (hematological status, clinical chemistry, see section 5.5.2)
- *PK samples only for a subgroup (see section 5.5.1.5)*
- Last IMP administration at site for all patients
- Drug return / accountability
- Diary collected and checked
- PASI (see section 5.5.1.1)
- PGA (see section 5.5.1.2)
- BSA (see section 5.5.1.3)

Trial Day 112 (week 16, visit 6, Follow-up) (End of Study, EoS)

- *Photographic documentation only for a subgroup (see section 5.5.1.4)*
- Check concomitant therapy and adverse events
- Physical examination (see section 5.5.5)
- Record vital signs (see section 5.5.3)
- Urinalysis(see section 5.5.2)
- Collection of samples for determination of laboratory parameters (hematological status, clinical chemistry, see section 5.5.2)
- PASI (see section 5.5.1.1)
- PGA (see section 5.5.1.2)
- BSA (see section 5.5.1.3)

The patients must be present at site for approximately 60 minutes on Screening and Day 1, 45 minutes on Day 28 and 56, 60 minutes on Day 84 and 45 minutes on Day 112.

The above mentioned time will be extended for 15 minutes for patients with photographic documentation on each visit.

The above mentioned time will be extended on Day 1 and Day 84 for 120 minutes for patients with PK sampling.

Early Termination Visit

Patients who discontinue early from the trial should, if possible, have an Early Termination Visit. This visit should take place as soon as possible after the patient stops taking IMP. The observations and procedures scheduled for Visit 5 (End of Treatment) should be performed at the Early Termination Visit.

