5.5.2 Measurement of safety parameters

Relevant medical history of the past five years and adverse events will be recorded.

The following laboratory parameters will be collected at every visit (except serology):

Table 4: Laboratory Parameter per visit:

Parameter	Screening	Day 1	Day 28 / 56	Day 84 (EoT)	Day 112 (FU)
Serology					
Hepatitis A IgG-antibody-test	X	--	--	--	--
Hepatitis A IgM-antibody-test	X	--	--	--	--
Hepatitis B core antibody-test	X	--	--	--	--
Hepatitis B surface antibody-test	X	--	--	--	--
Hepatitis B surface antigen-test	X	--	--	--	--
Hepatitis C virus antibody-test	X	--	--	--	--
HIV-1 antibody-test	X	--	--	--	--
HIV-2 antibody-test	X	--	--	--	--
Hematology					
RBC	X	X	X	X	X
WBC* including differential	X	X	X	X	X
Hemoglobin	X	X	X	X	X
Hematocrit	X	X	X	X	X
MCH	X	X	X	X	X
MCV	X	X	X	X	X
MCHC	X	X	X	X	X
Platelets	X	X	X	X	X
Clinical Chemistry					
AST (GOT)	X	X	X	X	X

Parameter	Screening	Day 1	Day 28 / 56	Day 84 (EoT)	Day 112 (FU)
ALT (GPT)	X	X	X	X	X
γGT	X	X	X	X	X
AP	X	X	X	X	X
Creatinine	X	X	X	X	X
Total bilirubin	X	X	X	X	X
CRP	X	X	X	X	X
hCG serum	X	--	--	--	--
Urine					
Urine dip stick test**	X	X	X	X	X

* including lymphocyte, neutrophils count, and eosinophils

** leukocytes, nitrite, pH, protein, glucose, ketones, urobilinogen, bilirubin, blood/hemoglobin

Hematological status, serology and clinical chemical parameters will be determined by LKF, [name]. Urinalyses will be performed at the sites using a dipstick test (Medi-Test®, Combi 10L, Macherey-Nagel, Dueren, Germany). Approximately 19.2 ml of blood will be withdrawn at each visit with laboratory analysis (in total approximately 116 mL per patient). For the PK subgroup additional 24.5 mL will be withdrawn on day 1 and day 84 (in total 49 mL per patient).

Spontaneously noted complaints will be recorded with duration, intensity and probability of a correlation with the IMP (see section 7.3., evaluation of adverse events).

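### IMP is re-dispensed on Day 28 and Day 56 with no scheduled pregnancy test since Day 1, and the footnote on test timing is ambiguous

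*Protocol*

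**What the plan says.** - **Footnote a** (protocol Appendix A, same wording in SAP Table 2): "A serum pregnancy test will be done for all women at screening and urine test for all other visits".
- **The row it annotates**, "Pregnancy test in female patients", has an X at Screening, Day 1 and Day 84. Day 28, Day 56, Day 112 and the unscheduled visit are blank. The SAP row has the same pattern.
- **Visit lists** (protocol 5.5.1): a serum test at screening, and a urine pregnancy test on Day 1 and Day 84. The shared Day 28/Day 56 list and the Day 112 list have urinalysis only.
- **Other laboratory items** (protocol 5.5.2, Table 4): serum hCG at screening only. The dipstick covers "leukocytes, nitrite, pH, protein, glucose, ketones, urobilinogen, bilirubin, blood/hemoglobin", so it does not detect pregnancy.
- **Dispensing:** the Day 28/Day 56 list ends with "Dispensing of IMP and diary". Section 5.4 adds: "The IMP will be packed in kits, 1 kit per patient per week".
- **Consequence:** pregnancy is among the criteria in 5.3.5.2 that must end participation, and 7.4 calls for immediate withdrawal.

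**The concern.** There are two linked points.

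The first is wording. Read literally, footnote a asks for a urine pregnancy test at every visit after screening. Read as naming the type of test, it asks only for urine rather than serum at the other marked visits. Two sites could follow different schedules in good faith.

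The second does not depend on how the footnote is read. The row and visit lists require a negative urine test before the first dose but none before either re-supply. The only on-treatment test after Day 1 falls at the visit where dosing ends. A pregnancy that begins early in treatment, and that nobody suspects, could go undetected by any scheduled test until the course is essentially complete. The withdrawal rule would then have no scheduled test behind it for the period in which it could limit exposure.

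**Working it through.** The plan states no figure to reproduce. The check sets the sources side by side and counts days.

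| Visit | Footnote a, literal | Flow-chart row | 5.5.1 list | IMP dispensed | Days since last test, on the row |
|---|---|---|---|---|---|
| Screening | serum | X | serum | no | – |
| Day 1 | urine | X | urine | yes | – |
| Day 28 (±2) | urine | blank | none | yes | 28 − 1 = 27 (25 to 29) |
| Day 56 (±2) | urine | blank | none | yes | 56 − 1 = 55 (53 to 57) |
| Day 84 (+5) | urine | X | urine | no, last dose on site | 84 − 1 = 83 (max 89 − 1 = 88) |
| Day 112 (±2) | urine | blank | none | no | – |

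**Number of urine tests after screening.** Literal footnote: 5. Row and lists: 2.

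**Effect of the window.** SAP Table 2 gives Day 84 as ±5 where the protocol has +5. The interval from Day 1 is then 79 − 1 = 78 to 89 − 1 = 88 days.

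**Interval with tests on Day 28 and Day 56.** Nominal gaps are 27, 28 and 28 days. Maxima are 30 − 1 = 29, 58 − 26 = 32 and 89 − 54 = 35 days.

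**Supply affected.** The documents do not say how many weekly kits are handed out at each visit. If each visit covers the weeks to the next, weeks 5 to 12, or 8 of 12, are supplied with no test since Day 1.

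**Illustration of how many pregnancies.** Tests on Day 28 and Day 56 can catch only conceptions before Day 56, a span of 56 − 1 = 55 days. The number of women of childbearing potential is not given; I assume 15 to 60. As a perfect-use illustration, take 1 pregnancy per 100 woman-years, the threshold in protocol 3.2.

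- Per woman: 55/365 × 0.01 = 0.0015, about 0.15%.
- 15 women: 15 × 0.0015 ≈ 0.02. 60 women: 60 × 0.0015 ≈ 0.09.
- With an assumed 14-day lag before a urine test turns positive (55 − 14 = 41 days): 15 × 41/365 × 0.01 ≈ 0.02, and 60 × 41/365 × 0.01 ≈ 0.07.

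**The case against.** The strongest reply has three parts.

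**The footnote belongs to one row.** Read as naming the test type, nothing conflicts, and the visit lists confirm that reading. This largely stands. A reader might infer a contradiction in the schedule, or three missed tests per completing woman. The documents do not support that: the row and lists agree with each other in both versions of the chart. What remains is an ambiguity worth removing.

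**Nothing in the documents requires a test at each dispensing.** Section 3.2 cites ICH M3 for contraceptive methods, not for a testing interval. Reproductive-risk data are left to the Investigator's Brochure. This also stands. A reader might infer a known fetal hazard or a breached requirement, and neither can be shown from these documents. The case for interim tests rests only on the protocol's own withdrawal rule and on the low cost.

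**Pregnancy control is already layered.** The plan has screening and pre-dose tests, highly effective contraception, periodic confirmation of abstinence, adverse-event checks at each visit, discretionary unscheduled visits, a test at the Early Termination Visit, and follow-up of any pregnancy to outcome. These reduce the risk but do not fill the gap. Adverse-event checks and unscheduled visits depend on suspicion arising. The Early Termination test comes after dosing has stopped, and outcome follow-up comes after exposure. The abstinence check has no entry of its own in the flow chart or the visit lists.

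**Conclusion.** The point holds as a minor safety improvement. On the row and visit lists, IMP is re-dispensed twice with no scheduled pregnancy test since Day 1. The next test, 83 days later (88 at most), could prevent no more than the final dose. Footnote a is ambiguous and, read literally, would already require the missing tests.

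The efficacy analysis is unaffected. The expected count is small: about 0.02 to 0.09 conceptions over the 55 days, given 15 to 60 women of childbearing potential. A reader might take these figures as upper bounds because the required Pearl Index is below 1. They are not. Section 3.2 ties that rate to consistent and correct use, and inclusion criterion 4 also allows abstinence, for which no rate is stated. They are perfect-use illustrations under an assumed number of women.

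The interval finding rests only on the schedule. The 8-of-12-weeks figure also assumes that each visit supplies the kits up to the next.

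**What to change.** 1. Add a urine pregnancy test on Day 28 and Day 56, read before IMP is dispensed, to the row in Appendix A, to the row in SAP Table 2 and to the shared Day 28/Day 56 list in 5.5.1.
2. Reword footnote a in both documents: *serum test for all women at screening; urine test at the other visits marked X (Day 1 and Day 84: all women; Day 28 and Day 56: women of childbearing potential)*. Naming the group matters because the row and the present footnote cover all women, including those who are post-menopausal or sterilized. Inclusion criterion 4 already requires women of childbearing potential to be identified at screening.
3. Optional: a Day 112 test, nominally the end of the 28-day post-dose contraception period, since completers have no scheduled test after Day 84.

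**Cost.** Two urine strips per woman of childbearing potential, at visits where urine is already collected, and edits to two rows, two footnotes and one visit list. Under protocol section 8, a change with ethical or medical implications is a substantial amendment needing approval, and an added safety test may qualify. With V2.0 dated October 2018 and the planned period ending in March 2019, it would reach only patients still on treatment.

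If the sponsor keeps the present frequency, the footnote should instead limit urine tests to the visits now marked. That removes the ambiguity but leaves the 83-day interval.
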